#### **8.4 Methods and Timing for Assessing, Recording, and Analyzing Safety Parameters**

At each encounter, standardized adverse event (AE) monitoring forms will be completed. At any point during the study period an adverse event is identified, it will be recorded in the participant research record along with the time/place of the event. The study physician will be immediately notified and the participant evaluated either by phone (if participant is not on site) or face-to-face (if participant is on site). Depending on the physician assessment, further evaluation maybe performed such as scheduling additional visits, further lab work, exam, or referral to the emergency department. Details about the safety parameters will be recorded and entered into a database. Comparisons between the 2 groups will be conducted to assess overall and between group differential safety.

#### **8.5 Adverse Events and Serious Adverse Events**

During the screening process, if the participant is identified to have a problem requiring medical attention such as severely elevated blood pressure, they are referred to their primary care physician or the emergency room. The primary care physician will be notified of screening results by mail upon the participant request. Adverse events will be reported to the Emory IRB, the data safety monitoring board (DSMB), the NIH funding agency, and the primary care provider of the participant. If the participant does not have a primary care provider, they will be referred to one. The timing of reporting depends on whether the adverse event is expected, is serious or not, and whether it suggests that other participants are at higher risk of harm. As shown in the flow diagram, any subject who develops a serious adverse event (SAE) requiring emergency medical care during the conduct of the study protocols will be referred for immediate medical care at the local hospital and intervention will be stopped. Subjects will be subsequently referred back to their primary care physician for ongoing hypertension care. SAEs will be reported to the above-named agencies within 24 hours of their discovery. Other adverse events (non-serious) will be reported within 2 weeks of their discovery. The flow of AE and SAE is shown in the next figure (**Figure 2**). Unexpected AE will be rated by the PI and the physician co-investigators as definitely, probably, or possibly related to research participation.

Figure 2: Serious Adverse Event/Adverse Event Process Flow

## **8.6 Incidental findings**

Incidental blood chemistry abnormalities, such as elevated blood sugar, will be reported to the subject and primary care provider. Incidental findings on brain imaging such as brain masses, prior stroke, and hemangiomas, will be evaluated by the PI and [name] (the study neurologist) and relayed to the subject and her/his provider. Similarly, incidental carotid ultrasound findings such as carotid stenosis will be evaluated by the PI and [name] (the study cardiologist) and also relayed to the subject and his/her provider. In the unlikely event that an incidental finding requires immediate attention such as bleeding on MRI, urgent care will be provided in a facility of the participant's preference.

## **8.7 Reporting Procedures**

Expected side effects described within the safety parameters will be reported to the IRB, DSMB and NIA as part of ongoing progress. SAEs will be reported to the DSMB, NIH and IRB within 24h as shown in figure 2. A detailed report will follow within 7 days, and then a final resolution report will be sent. Other causes or existing health issues will be investigated and ruled out as the inciting factor prior to the determination of an adverse reaction. Unexpected AE will be reported to the above agencies within 2 weeks.

## **8.8 Follow-up for Adverse Events**

With the permission from the participant, we will contact the participant's primary care doctor and help him/her get medical follow-up. Adverse events that require follow-up such as increased potassium or increased creatinine will be monitored until resolved or are further followed by the primary care provider. If emergency care or hospitalization was necessary, the study physician will conduct a follow-up phone or face-to-face evaluation. If the event requires intervention discontinuation (see section 9 below), the participant will be transitioned to his usual antihypertensive medication and referred back to the primary care provider. They will be followed for 2 months post-withdrawal. They will also be invited to perform the final visit evaluation including all study procedures planned for that visit.

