clinical practice. Possible side effects include: dizziness, cough (lisinopril), weakness, fatigue, lower extremity edema and constipation (amlodipine), and hypotension. Renal failure and hyperkalemia are also potential complications of candesartan and lisinopril. HCTZ may cause renal failure, volume depletion, and hypokalemia. Lisinopril may cause a dry cough and angioedema. Beta blockers may be associated with weakness and bradycardia. Adverse events will be queried at each visit. Alternatives to antihypertensive medications include no therapy, which is not safe or ethical in patients with hypertension. Drug-drug interaction will be assessed by the study physician. If there is contraindication to use the candesartan or lisinopril and one of the other participant's medications then he/she will not be able to enroll in the study. If the contraindication is between an add-on agent (amlodipine, metoprolol, or HCTZ) then the participant will be enrolled but we will avoid using that agent as an add-on as described in section 5.3. Use of lithium is a contraindication for both lisinopril and candesartan and hence lithium users are excluded. The following combinations of medications are contraindicated for the add-on drugs: Simvastatin >20 mg with amlodipine, reserpine with metoprolol, and clonidine with metoprolol.

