## 8.2 Specification of Safety Parameters

The study medications may lead to adverse drug reactions (rash, edema, and in severe cases anaphylaxis) and uncomfortable side effects. If this occurs, the study medication will be discontinued and the subject's primary care provider notified. If the subject cannot tolerate the study medication, the study medication will be stopped and he/she will be referred to their primary care physician for ongoing hypertension treatment. The participant will however be continued in the study and asked to undergo the final visit evaluations. Subjects will be monitored carefully for symptoms, blood pressure control, and blood chemistry abnormalities during treatment, as described in the methods section above. A physician (PI) and trained personnel will be available at all times to respond to subjects' concerns. In the event of an emergency, resuscitation equipment is readily available in all the research areas where subjects are evaluated. Antihypertensive medications will also be adjusted up/down to maintain blood pressure below 140/90 mm Hg and above 100/45 mm Hg or at the discretion of the study physician for maintaining safety. For example, if blood pressure readings are high at their study visits but normal/low at home or the subject reports orthostatic dizziness the clinician will use his judgment to change the dosage of the study meds.

The subject's primary care physician will be informed of study plans. Frequent monitoring will include visits, blood pressure checks, laboratory testing and phone contact. Blood testing for kidney function and electrolytes (potassium) will be performed at baseline, 1, 3, 6 and 12 months. If needed, additional calls, visits, or laboratory testing will be conducted as decided by the PI and /or the primary care physician. If symptoms develop during any of the evaluations, procedures will be terminated immediately. The experimental procedures will be conducted in a well-supervised facility and subjects will be under constant observation by skilled professionals. Those who could not continue on the study medications will be asked to return for collection of outcome measure if they agree to return for the final assessment visit.

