## **9. INTERVENTION DISCONTINUATION**

A subject may choose to withdraw from the study for any reason. The investigators may also request that the subject withdraw from the study, for safety or other reasons. Withdrawn participants will continue to be monitored by the study personnel for 2 months after the event if possible and invited to complete the final visit evaluation. The criteria for discontinuing a subject's participation include:

- (1) the subject's request,

- (2) serious adverse events that requires un-blinding,
- (3) new stroke, transient ischemic attack, or myocardial infarction that limits ability to complete the study
- (4) Symptomatic dysrhythmia
- (4) anaphylaxis or allergic reaction to study medications,
- (5) disturbing and persistent cough ( transient mild cough is not a discontinuation criterion unless participant requested it),
- (6) inability to participate due to relocation or other personal reasons,
- (7) renal failure (increase in serum Creatinine above 2.5 mg/dl) or hyperkalemia (greater than 5.8 meq)

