### **10.2 Randomization**

The study un-blinded biostatistician will provide oversight of randomization fidelity and blinding. To ensure equal distribution between the 2 groups on important confounders, we will use block randomization with stratification on:

- (1) race, (white, non-white).
- (2) number of antihypertensive medications (2 or less vs >2).

Randomization will occur in a 1:1 allocation. Four separate randomization lists will be prepared (race=white, medications=2 or less; race=white, medications>2; race-non-white, medications=2 or less; race=non-white, medications>2). Randomization will use a computerized random number generator (SAS, V9.3); the blocking number will not be revealed to investigators or research staff. Each randomization list will include the treatment group allocation, a unique allocation sequence number, and a blank field (to complete with subject study ID as randomization occurs). Randomization lists will be provided to the IDS Pharmacy. Only the pharmacy and the un-blinded statistician will have access to the randomization lists. As the pharmacist is notified that an individual subject is eligible for randomization to a given stratum, the pharmacist will select the appropriate randomization list, complete the subject ID, and prepare the appropriate blinded study product. The pharmacist will enter the subject ID, date of product randomization, and the unique allocation sequence number on a web-based data form. The statistician will monitor appropriateness of randomization (eligibility criteria met, correct stratum used, next allocation sequence used) in real time; incorrect randomizations will be immediately recorded as protocol deviations and reported to the principal investigator (in a blinded fashion).

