#### 10.4 Outcomes

Table 3 provides a list of main outcomes. Other Analyses' variables: Logical memory, digit span, DSST, WMH volume, regional brain measures

**Table 3:** Independent, primary and secondary outcomes and other variables to be used in the analyses

Independent:	Randomization Group (Candesartan vs Lisinopril)
Primary outcome:	Executive function (EXAMINER score)
Secondary Imaging outcomes:	Perfusion, CO2 VR, VMR, FA, MD, DTT t-scores, rs-fMRI
Mediators:	CIMT, stiffness, inflammatory markers, EPC
Tertiary outcomes:	memory, digit span, DSST, WMH volume, regional brain measures
Stratification variable:	Race, number of antihypertensive medications
Covariates:	Prior stroke and prior use of ACEI/ARB
Safety:	AE, SAE, incident dementia

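### Section 8.8 sends participants stopped for an adverse event back to their usual antihypertensive without exception; for prior ACE inhibitor or ARB users this can mean the same drug or class, and sections 8.2 and 8.5 describe a different route.

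*Combined protocol and SAP*

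**What the plan says.** Section 8.8 (Follow-up for Adverse Events) opens its rule with "If the event requires intervention discontinuation (see section 9 below" and continues that "the participant will be transitioned to his usual antihypertensive medication and referred back to the primary care provider". It then provides two months of follow-up and an invitation to the final visit.

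The list it points to, section 9, contains among other reasons "anaphylaxis or allergic reaction to study medications", a disturbing and persistent cough, and "renal failure (increase in serum Creatinine above 2.5 mg/dl) or hyperkalemia (greater than 5.8 meq". Section 8.1 (Potential Risks) states: "Renal failure and hyperkalemia are also potential complications of candesartan and lisinopril". It also lists dry cough and angioedema under lisinopril.

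Two other sections deal with overlapping events. Section 8.2 has the study drug discontinued and the primary care provider notified after an adverse drug reaction. If the drug cannot be tolerated, it is stopped and "he/she will be referred to their primary care physician for ongoing hypertension treatment". Section 8.5 has the intervention stopped after a serious adverse event needing emergency care, followed by referral to primary care for blood pressure treatment. Neither section tells staff to resume the earlier regimen.

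On who can be affected, section 4.1 admits treated hypertensives who agree to taper, with no restriction by drug class. Table 3 in section 10.4 lists as covariates "Prior stroke and prior use of ACEI/ARB".

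**The concern.** An instruction that applies to every reason for stopping does not separate events unrelated to the study drug from suspected reactions to it. If the usual regimen contained lisinopril, candesartan or a related drug, following 8.8 as worded can put the participant back on the drug or class under suspicion. That is a participant-safety matter.

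There is also an operational problem. Staff handling one event, such as an allergic reaction, find one destination in 8.8 and another in 8.2 or 8.5, and nothing says which section governs. Two participants with the same event could be handled differently, each in line with the protocol.

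**Working it through.** The plan gives no figure to reproduce here. The check is a comparison of sections, followed by one comparison of thresholds.

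**1. What triggers 8.8.** Any event requiring discontinuation under section 9. No event type is carved out.

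**2. What the usual medication means.** Section 8.8 does not define it. Section 8.3, on participants whose taper runs into difficulty, explains usual doses as those taken before the study. Reading 8.8 as a return to the pre-trial regimen is therefore the natural one.

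**3. Whether that regimen can contain the same drug or class.** It can. Section 4.1 sets no class restriction, and sections 10.4 and 10.5 plan to adjust for prior ACE inhibitor or ARB exposure, so such participants are expected. Section 4.2(1) excludes intolerance to candesartan or lisinopril, but it is an entry criterion and cannot act on a reaction that first appears during the trial.

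**4. Which section 9 reasons the protocol itself links to study drug.**

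| Section 9 reason | Link elsewhere in the protocol |
|---|---|
| Renal failure | 8.1, both study drugs |
| Hyperkalemia | 8.1, both study drugs |
| Persistent cough | 8.1, lisinopril only |
| Anaphylaxis or allergic reaction | Criterion names study medications; 8.2 lists rash, edema and anaphylaxis as possible reactions |

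**5. Routes after the stop.**

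| Section | Event | Stated route |
|---|---|---|
| 8.2 | Drug reaction | Stop; notify primary care |
| 8.2 | Intolerance | Stop; refer to primary care |
| 8.5 | Serious event needing emergency care | Hospital care; stop; refer to primary care |
| 8.8 | Any event requiring a stop under section 9 | Move to usual antihypertensive; refer to primary care |

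The step to the usual antihypertensive appears only in 8.8. Sections 8.2 and 8.5 do not forbid it; they leave it out.

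**6. Stopping limits against entry limits.** Section 4.2(3) excludes potassium above 5.5 or creatinine above 1.99 mg/dl. Section 9 stops above 5.8 or above 2.5 mg/dl.

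- Potassium: 5.8 − 5.5 = 0.3 above the entry limit, at least.
- Creatinine: 2.5 − 1.99 = 0.51 mg/dl above the entry limit, at least.

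The potassium units are printed differently in the two sections; I take them to be the same scale. I read the creatinine criterion as a level. Read as a rise of that size, it would lie further above the entry limit.

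So a participant stopped on either criterion is at a value on which the protocol would not have admitted them to receive either study drug. Section 8.8 follows abnormal potassium and creatinine until they resolve or primary care takes over, but it does not make the change of medication wait for that.

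**7. Allocation.** Section 5.1 blinds investigators, staff and participants. Section 10.2 says: "Only the pharmacy and the un-blinded statistician will have access to the randomization lists". Section 9(2) refers to serious events that require un-blinding, so un-blinding is foreseen for some stops. The visible text does not say for which stops, or who is told. Figure 2, the adverse event flow, is not shown in the copy reviewed.

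**The case against.** The best defense is that 8.8 does not operate alone. Section 8.4 has the study physician notified at once of any adverse event and the participant evaluated, with further visits, laboratory work or referral as judged necessary. Section 8.8 itself monitors potassium and creatinine and hands the participant to primary care in the same sentence. Section 8.2 deals specifically with drug reactions, including anaphylaxis. A physician is unlikely to resume a suspect drug mechanically. All of this stands and lowers the practical risk. None of it is written as a condition on the return to usual medication, and it does not remove the conflict between sections.

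Several stronger readings are tempting and are not supported:

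- *Everyone who stops is exposed.* Untreated hypertensives are eligible and have no usual drug. Those whose earlier regimen held no ACE inhibitor or ARB face no return to the same class.
- *Angioedema is a listed stop reason.* Section 8.1 names it for lisinopril, but section 9 does not; it enters only if classed as an allergic reaction. Conversely, 8.1 does not name allergic reaction.
- *A count can be given.* Assuming that 30–60% of participants are prior users and 3–10% of the 160 enrolled stop for such reactions gives 160 × 0.03 × 0.30 = 1.4 to 160 × 0.10 × 0.60 = 9.6. Both rates are invented. The product also ignores 1:1 allocation: if each prior user took one class, half would have been assigned the other, giving about 0.7 to 4.8. It further treats the two rates as independent, although 4.2(1) removes people with known intolerance. Neither range is evidence.
- *Allocation is never disclosed after a stop.* Section 9(2) contemplates un-blinding and Figure 2 cannot be seen, so this cannot be asserted.
- *The safety comparison is compromised.* The event that led to the stop is already recorded, and section 10.5 compares numbers of events by group. A later recurrence on the resumed drug may be harder to attribute, but it does not erase the first event.

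**Conclusion.** The point holds as a conflict in the text. Section 8.8 gives an unconditional instruction that, for prior ACE inhibitor or ARB users, can return a participant stopped for a suspected study-drug reaction to the same drug or class. The conflict is clearest for renal failure and hyperkalemia, because the protocol attributes both to both study drugs and the stopping values exceed its own entry limits. Sections 8.2 and 8.5 describe a different route for overlapping events.

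This rests on reading the usual medication as the pre-trial regimen, which 8.3 supports, and on the absence of any overriding step in the flow diagram that is not shown. The number affected cannot be derived from the documents. No effect on the primary EXAMINER analysis is claimed. The point deserves correction because it bears on participant safety and is inexpensive to resolve.

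**What to change.** Reconcile section 8.8 with 8.2, 8.5, section 9 and the entry limits in 4.2, so that one consistent route applies when the stop is for a suspected reaction to study drug. The sponsor and responsible physicians should decide what that route is; this review proposes none.

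In the same revision, make the text of 8.8, section 9(2), section 10.2 and Figure 2 agree on whether allocation is disclosed in these cases. Stopped participants are still asked to complete final assessments, and the primary outcome is a test they perform themselves, so the answer should be explicit whichever way it goes.

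The cost is protocol wording. Sample size, visit schedule and analysis model are unchanged.

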## **8.9 Safety Monitoring**

Safety procedures will be implemented in accordance with NIH safety policies for clinical trials. The safety monitoring will be conducted by the PI and a Data and Safety Monitoring Board (DSMB). The DSMB is comprised of 4 members (see section 14) in addition to a statistician. Once an SAE has been identified, it will be reported to the Emory-IRB. The grant program officer at NIA will also be notified. The DSMB will be asked to review the event. Once a year, the DSMB will meet to review progress of the trial (recruitment and follow-up, protocol violations), assess the safety of the protocol, and address any issue that limits the study success. A report template will be drafted prior to initiation of recruitment. The report will include tabulation by treatment group of all AE and SAEs to be reviewed by the DSMB. If concerns arise about safety issues, the DSMB may request additional data and propose specific analyses. A report summarizing the discussions and recommendations for continuation of the trial will be generated from the DSMB meeting and provided to the IRB and NIH funding institute.

## **9. INTERVENTION DISCONTINUATION**

A subject may choose to withdraw from the study for any reason. The investigators may also request that the subject withdraw from the study, for safety or other reasons. Withdrawn participants will continue to be monitored by the study personnel for 2 months after the event if possible and invited to complete the final visit evaluation. The criteria for discontinuing a subject's participation include:

- (1) the subject's request,

- (2) serious adverse events that requires un-blinding,
- (3) new stroke, transient ischemic attack, or myocardial infarction that limits ability to complete the study
- (4) Symptomatic dysrhythmia
- (4) anaphylaxis or allergic reaction to study medications,
- (5) disturbing and persistent cough ( transient mild cough is not a discontinuation criterion unless participant requested it),
- (6) inability to participate due to relocation or other personal reasons,
- (7) renal failure (increase in serum Creatinine above 2.5 mg/dl) or hyperkalemia (greater than 5.8 meq)

### **10.2 Randomization**

The study un-blinded biostatistician will provide oversight of randomization fidelity and blinding. To ensure equal distribution between the 2 groups on important confounders, we will use block randomization with stratification on:

- (1) race, (white, non-white).
- (2) number of antihypertensive medications (2 or less vs >2).

Randomization will occur in a 1:1 allocation. Four separate randomization lists will be prepared (race=white, medications=2 or less; race=white, medications>2; race-non-white, medications=2 or less; race=non-white, medications>2). Randomization will use a computerized random number generator (SAS, V9.3); the blocking number will not be revealed to investigators or research staff. Each randomization list will include the treatment group allocation, a unique allocation sequence number, and a blank field (to complete with subject study ID as randomization occurs). Randomization lists will be provided to the IDS Pharmacy. Only the pharmacy and the un-blinded statistician will have access to the randomization lists. As the pharmacist is notified that an individual subject is eligible for randomization to a given stratum, the pharmacist will select the appropriate randomization list, complete the subject ID, and prepare the appropriate blinded study product. The pharmacist will enter the subject ID, date of product randomization, and the unique allocation sequence number on a web-based data form. The statistician will monitor appropriateness of randomization (eligibility criteria met, correct stratum used, next allocation sequence used) in real time; incorrect randomizations will be immediately recorded as protocol deviations and reported to the principal investigator (in a blinded fashion).

